$$r_{d1,d2} \sim \text{Binomial}(n_{d1,d2}, \pi_{12,d1,d2})$$

where $r_{d1,d2}$ denotes the random variable describing the observed number of DLTs in $n_{d1,d2}$ patients at the dose combination d_1, d_2 .

Since a Bayesian approach is applied, prior distributions f for each of the parameter vectors $\theta_1=(\log(\alpha_1),\log(\beta_1))$, $\theta_2=(\log(\alpha_2),\log(\beta_2))$ and for the interaction term η need to be specified.

The prior distributions for θ_k will be specified as a mixture of two bivariate normal distributions,

$$f(\theta_k) = a_{1,k} f_1(\theta_k) + a_{2,k} f_2(\theta_k)$$

with

$a_{1,k}$, $a_{2,k}$ the prior mixture weights ($a_{1,k} + a_{2,k} = 1$), $k = 1,2$ and

$f_i(\theta_k) = \text{MVN}(\mu_{ik}, \Sigma_{ik})$ a bivariate normal distribution with mean vector μ_{ik} and covariance matrix Σ_{ik} where

$$\Sigma_{ik} = \begin{pmatrix} \sigma_{ik,11}^2 & \sigma_{ik,11}\sigma_{ik,22}\rho_{ik} \\ \sigma_{ik,11}\sigma_{ik,22}\rho_{ik} & \sigma_{ik,22}^2 \end{pmatrix}$$

Mixture prior distributions have the advantage that they allow for specification of different logistic dose-toxicity curves, therefore making the prior more robust.

A weakly informative normal prior distribution will be used for η .

The estimated probability of DLT $\pi_{12,d1,d2}$ at each dose combination d_1, d_2 from the model will be summarized using the following intervals:

- * Under dosing: [0.00, 0.16)
- * Targeted toxicity: [0.16, 0.33)
- * Over dosing: [0.33, 1.00]

The BLRM recommended dose combination for the next cohort is the combination with the highest posterior probability of the DLT rate falling in the target interval [0.16, 0.33) among the dose combinations fulfilling the EWOC principle. Per EWOC it should be unlikely (<25% posterior probability) that the DLT rate at the dose combination will exceed 0.33. However, the maximum allowable dose increment for the subsequent cohort will be no more than 100 % for each drug.

The MTD may be considered reached if one of the following criteria is fulfilled:

1. The posterior probability of the true DLT rate in the target interval [0.16 – 0.33) of the MTD is above 0.50, or
2. At least 6 patients have been treated at the MTD.

Prior derivation

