7.7 DETERMINATION OF SAMPLE SIZE

No formal statistical power calculations to determine sample size were performed for this study. Approximately 148 patients (including patients at MTD) will be expected for this trial based on the number of dose levels/cohorts that are tested. Fewer or more patients might be needed based on the recommendation of the SC and BI Trial Team and the criteria specified (see [Section 7.1](#)).

Dose finding cohorts A, B, C and D:

Approximately 12 patients in cohorts A, B, C and D (dose finding) will be needed to define a MTD. In total, approximately 48 patients will be needed for the dose finding cohorts. However, the actual number of patients will depend on the number of dose levels tested.

Based on the simulation study to evaluate operating characteristics of the BLRM (see [Appendix 10.6](#)), approximately 12 patients (in mean) are expected to be treated in the dose finding cohort A for the model to have reasonable operating characteristics relating to its MTD recommendation (see [Appendix 10.6](#)).

Considering the toxicity profile of individual compounds, we can assume the same number of patients will be needed in the dose finding cohorts B, C and D (dose finding).

Expansion cohort E:

In expansion cohort E, 20 patients will be treated at the MTD/RP2D.

Assuming a true objective response (OR) rate of 60%, a sample size of 20 patients leads to a probability of 87% of observing at least 10 ORs. If the true OR rate is higher, i.e. 80%, the probability of observing at least 10 ORs is higher than 99%. The probability to observe a false positive signal, i.e. to observe at least 8 ORs if the underlying true OR rate is 20%, is only 3%. [Table 7.7: 1](#) summarizes the probabilities of observing certain OR rates based on different assumptions on underlying OR rates.

Table 7.7: 1 Objective response rates for Cohort E

True OR rate	Patients	Probability to observe at least									
		7 events	8 events	9 events	10 events	11 events	12 events	13 events	14 events	15 events	
60%	20	0.99	0.97	0.94	0.87	0.76	0.60	0.42	0.25	0.13	
80%	20	>0.99	>0.99	>0.99	>0.99	>0.99	0.99	0.97	0.91	0.80	
20%	20	0.09	0.03	< 0.01	< 0.01	< 0.01	< 0.01	< 0.01	< 0.01	< 0.01	

An OR rate of 60% would be considered clinically relevant in NSCLC patients (cohort E).

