10.6 STATISTICAL APPENDIX

A Bayesian logistic regression model with overdose control will be used to guide dose escalation/ de-escalation in cohorts A, B, C and D(dose finding). The BLRM is introduced in [Section 7.1](#), which also specifies the prior for the model in cohort A. The priors for other dose finding cohorts (B, C and D(dose finding)) will be documented in the TSAP. After patients in each dose group have completed at least one course of treatment, the prior distributions will be updated through Gibbs sampling procedures with the accumulated DLT data from the MTD evaluation period. Posterior probabilities for the rate of DLT will be summarised from BLRM. Selection of the next dose combinations will be based on these probabilities as well as on other safety and laboratory data.

The purpose of this statistical appendix is to present performance metrics (operating characteristics) that illustrate the precision of the design in estimating the MTD under various dose-toxicity relationships through computer simulation. These results are summarized in [Table 10.6: 3](#). In addition, recommendations of the next dose combination by the BLRM with overdose control principle are also provided under various hypothetical outcome scenarios in

early dose groups to show how it facilitates on-study dose-escalation decisions (see [Table 10.6: 1](#)).

Hypothetical data scenarios

Hypothetical data scenarios are shown in [Table 10.6: 1](#). These scenarios reflect potential on-study data constellations and related escalation as allowed by the model. For each scenario, the probability of target dose and overdose for the current dose combination, as well as the next potential dose combination and related probabilities of under-dosing, target dose, and over-dosing are shown.

For example, scenario 1 shows the example, that at the starting dose combination 150 mg abemaciclib and 1000 mg xentuzumab none of 3 patients experiences a DLT. Then, the BLRM allows treating patients at the same dose which is the maximum combination dose allows by the protocol.

Scenario 4 shows the example, that at the starting dose combination 150 mg abemaciclib and 1000 mg xentuzumab none of 6 patients experiences a DLT. Therefore, the MTD in this case would be the combination of 150 mg / 1000 mg.

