For each of these scenarios, 1000 trials were simulated. Each cohort consisted of 3 patients and dose escalation complied with the following rule:

- Escalate to the dose combination which maximises the probability of the targeted toxicity region and satisfies the overdose criterion

The MTD was considered reached if at least 6 patients have been evaluated at a dose combination which is the model's recommendation for the next dose-level cohort and for which the posterior probability of targeted toxicity was at least 50%. Or if in total 6 patients have been evaluated at a dose combination which is the model's recommendation for the next dose-level cohort.

It was then assessed how often a dose combination was declared as MTD with true DLT rate in the under-, targeted or over-dose range.

Furthermore, the average, minimum and maximum number of patients per trial and the average number of DLTs per trial are reported. Results are shown in [Table 10.6: 3](#) below.

Table 10.6: 3 Simulated operating characteristics for cohort A

Scenario	% of trials declaring a MTD with true DLT rate in				# Patients	# DLTs
	underdose	target dose	overdose	Stopped	Mean (Min-Max)	Mean (Min-Max)
1: Prior	43.7	54.3	0	2.0	10.86 (3, 21)	2.19 (0, 8)
2: High Tox	0	68.3	23.3	8.4	10.68 (3, 21)	3.10 (1, 9)
3: Low Tox	23.9	73.3	0	2.8	11.94 (3, 21)	1.75 (0, 7)
4: Low-High	3.9	55.1	38.9	2.1	12.10 (3, 21)	2.91 (1, 9)

In scenario 1, which reflects the case that the true dose-toxicity is aligned with prior means, almost all of the simulated trials (54%) that have found a MTD declared the MTD with true toxicity rate in the target interval. Few simulated trials (2.0%) have been stopped before declaring a MTD. None of trials declared a MTD with true DLT rate in the overdose interval.

In scenario 2 (high-toxicity scenario) 68% of the simulated trials that have found a MTD declared the MTD with true toxicity rate in the target interval and 23% declared a MTD with true DLT rate in the overdose interval. Few simulated trials (8%) have been stopped before declaring a MTD.

Scenario 3 (low-toxicity scenario) illustrates a behaviour similar to scenario 1.

Scenario 4, a mixture of the high toxicity and the low toxicity scenario, shows characteristics of both of these.

The mean patient numbers range from 10.68 patients (Scenario 2) to 12.10 patients (Scenario 4) and the maximum number of patients was 21. Therefore, the patient numbers are as expected.

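### The stopping rule written in protocol 7.1 and 10.6, started at 150/1000, gives about 6 to 9 patients in cohort A, not the roughly 12 on which section 7.7 rests its sample size and operating characteristics

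*Protocol*

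**What the plan says.** - **Sample size (protocol 7.7).** "approximately 12 patients (in mean) are expected to be treated in the dose finding cohort A for the model to have reasonable operating characteristics". The same number is assumed for B, C and D, giving about 48 for dose finding.
- **Source (protocol 10.6).** "The mean patient numbers range from 10.68 patients (Scenario 2) to 12.10 patients (Scenario 4) and the maximum number of patients was 21". The means in Table 10.6:3 are 10.86, 10.68, 11.94 and 12.10 for scenarios 1 to 4, from 1000 simulated trials each.
- **Stopping rule for the trial (7.1).** "The MTD may be considered reached if one of the following criteria is fulfilled": a posterior probability above 0.50 that the DLT rate lies in the target interval, or "At least 6 patients have been treated at the MTD".
- **Stopping rule in the simulation (10.6).** One alternative is 6 patients together with a target probability of at least 50%. The other is "Or if in total 6 patients have been evaluated at a dose combination which is the model's recommendation for the next dose-level cohort". The same text says "Each cohort consisted of 3 patients".
- **Dose levels (4.1.2.1).** Cohort A starts at 150/1000 (abemaciclib/xentuzumab, mg). The other two planned levels are lower, and escalation beyond the highest planned levels is ruled out.
- **Worked example (10.6, data scenario 4).** "none of 6 patients experiences a DLT. Therefore, the MTD in this case would be the combination of 150 mg / 1000 mg".

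**The concern.** A cohort that tolerates 150/1000 has nowhere higher to go. Table 10.6:1 keeps it there after 0/3 and 1/3 DLTs, and again after 0/6 and 1/6. It therefore meets the 6-patient criterion with its second group of three. A mean near 12 would need many cohorts to run well beyond that, which the written rule does not ask for.

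Section 7.7 uses the simulation for two things: the expected size of each dose-finding cohort, and the statement that the model performs reasonably at that size. If the simulated design is not the written one, neither statement is supported for the trial as described. The resulting RP2Ds are used downstream: cohort A's sets the dose for cohort E, and cohort D's for F, D1 and D2.

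**Working it through.** **1. The plan's own figures.** 4 × 12 = 48, and 12 is at the upper end of the printed range 10.68-12.10. The arithmetic from Table 10.6:3 to 7.7 is in order. The question is whether the table follows from the rule.

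**2. A check that needs no simulation.** By Table 10.6:1, at most 1 DLT in the first 6 patients at 150/1000 keeps 150/1000 as the recommendation, so the rule is met at 6. With p the true DLT rate at 150/1000 (Table 10.6:2), the chance of this is

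P6 = (1−p)^6 + 6p(1−p)^5.

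This is a lower bound on the share of cohorts stopping at 6. No simulated cohort exceeded 21 patients, so the mean can be at most 6·P6 + 21·(1−P6) = 21 − 15·P6.

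| Scenario | p | P6 | Largest possible mean | Printed mean |
|---|---|---|---|---|
| 1 | 0.150 | 0.377 + 0.399 = 0.776 | 9.4 | 10.86 |
| 2 | 0.31 | 0.108 + 0.291 = 0.399 | 15.0 | 10.68 |
| 3 | 0.10 | 0.531 + 0.354 = 0.886 | 7.7 | 11.94 |
| 4 | 0.20 | 0.262 + 0.393 = 0.655 | 11.2 | 12.10 |

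The printed means in scenarios 1, 3 and 4 cannot arise from the written rule started at 150/1000. Scenario 4 is the closest. A mean of 12.10 would need a stopping share of at most (21 − 12.10)/15 = 0.593, against at least 0.655. The simulation error of a share over 1000 trials is √(0.655 × 0.345/1000) = 0.015, too small to bridge that. This bound does not settle scenario 2.

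**3. Rebuilding the model.** The 5-parameter logistic model with the Table 7.1:3 prior matches the protocol's tables:
- Prior overdose probability at 150/1000: 0.096-0.098 (stated 0.098).
- Target and overdose probabilities after 0/3: 0.174 and 0.026 (stated 0.179 and 0.027).
- After 0/6: 0.114 and 0.008 (stated 0.116 and 0.009).
- The recommendations agree for the Table 10.6:1 states compared.

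**4. Cohort size under the written rule**, in groups of 3 from 150/1000:

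| Scenario | Mean patients | Stopping at exactly 6 | Printed mean |
|---|---|---|---|
| 1 | 6.4-7.2 | 78-92% | 10.86 |
| 2 | 7.8-9.2 | 41-68% | 10.68 |
| 3 | 6.2-6.5 | 89-97% | 11.94 |
| 4 | 6.8-7.7 | 66-86% | 12.10 |

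The ranges reflect a near-tie. After 2/6 DLTs, 150/750 and 150/1000 both have a target probability of about 0.475, so numerical noise decides whether the cohort stops or moves to the lower combination.

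**5. What could produce about 12?**
- Dropping 100/750 from the grid changes little: 6.5, 7.8, 6.2 and 6.9.
- Starting at 100/750 under the same rule gives about 9.4 to 11 across scenarios: nearer, but not a match.
- Requiring 6 patients at the dose plus either a target probability of at least 0.50 or 12 patients in total gives about 11.5 to 13.2 across runs.

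None of these is stated in the protocol. In 10.6 the second stopping alternative makes the first redundant, so a condition may have been lost in the text; that is an inference.

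**The case against.** **The text is permissive.** The MTD may be considered reached, the Steering Committee may recommend stopping, further patients may be added to confirm the estimate, and 7.7 allows for fewer or more. This stands: the rule allows a stop at 6 and does not impose one. It does not rescue the figure, because 7.7 cites a simulation that applied a fixed rule with no committee discretion.

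**The cause is unproven.** This also stands. A reader might infer that a different stopping rule was simulated. A different start is also possible: the simulated grid contains 100/750, which is not a planned cohort A level.

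**Six is not always the usual end.** In scenario 2 the share stopping at 6 is 41-68%, and the mean may reach about 9.

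**Safety.** A reader might infer that the written rule is much worse at rejecting a toxic top dose. The documents do not establish that. With assumed true DLT rates of 20%, 33%, 25% and 40% at 100/750, 150/750, 100/1000 and 150/1000, the 40% combination is named MTD in about 38-52% of cohorts under the written rule. With the 12-patient condition it is 27-30%. The gap depends on the same near-tie and on rates that are not in the protocol. Section 5.1.1 also has the MTD re-examined with the expansion data.

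**Cohorts B to D.** Multiplying the cohort A figure by four is not supported, because their priors are not given.

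**Conclusion.** The expected size in 7.7 does not follow from the rule, start and model the protocol states. For cohort A that design averages about 6 to 9 patients across the four scenarios, against the printed 10.68-12.10, and meets the rule at exactly 6 in at least 78%, 40%, 89% and 66% of cohorts. The contradiction in scenarios 1, 3 and 4 needs only the protocol's tables and a binomial probability. In scenario 2 it rests on the rebuilt model.

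The result assumes groups of 3, the Table 7.1:3 prior, the Table 10.6:2 rates, and stopping as soon as the criterion is met. For B to D it can be extended only under an assumption. With full borrowing of cohort A's data, the share stopping at 6 is at least 91% if A gave 0/6, 66-97% if 1/6 and 26-71% if 2/6, with a mean of at most 10.0.

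This is not evidence that any cohort did stop at 6 or that a selected dose is wrong; neither document gives the sizes achieved.

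**What to change.** 1. In 10.6, state the stopping rule, starting dose and dose grid actually simulated, and make 7.1 and 10.6 agree.
2. Re-run the simulation with the rule and 150/1000 start as written. Replace the patient numbers and operating characteristics in Table 10.6:3.
3. Restate 7.7: about 6 to 9 for cohort A, and a figure for B to D only under a stated prior. If about 12 is intended, write down the rule that produces it.
4. The SAP introduction says safety analyses followed each of cohorts A to D. Report the rule applied, the sizes reached, and the operating characteristics at those sizes.
5. Any illustration of the chance of selecting a toxic combination should be a range on declared, assumed DLT rates.

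The cost is protocol or report wording and one simulation run. Restating the expected size needs no patients. A 12-patient condition would not fit strictly within 48: at the upper mean of 13.2, four cohorts come to 4 × 13.2 = 52.8.

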8. INFORMED CONSENT, TRIAL RECORDS, DATA PROTECTION, PUBLICATION POLICY

The trial will be carried out in accordance with the Medical Devices Directive (93/42/EEC) and the harmonised standards for Medical Devices (ISO 14155, current version).

The trial will be carried out in compliance with the protocol, the ethical principles laid down in the Declaration of Helsinki, in accordance with the ICH Harmonized Tripartite Guideline for Good Clinical Practice (GCP), relevant BI Standard Operating Procedures (SOPs), the EU regulation 536/2014 the Japanese GCP regulations (Ministry of Health and Welfare Ordinance No. 28, March 27, 1997) and other relevant regulations.

Standard medical care (prophylactic, diagnostic and therapeutic procedures) remains in the responsibility of the treating physician of the patient.

The Investigator will inform the sponsor immediately of any urgent safety measures taken to protect the trial subjects against any immediate hazard, and also of any serious breaches of the protocol or of ICH GCP.

The Boehringer Ingelheim transparency and publication policy can be found on the following web page: trials.boehringer-ingelheim.com. The rights of the Investigator and of the sponsor with regard to publication of the results of this trial are described in the Investigator contract. As a rule, no trial results should be published prior to finalization of the Clinical Trial Report.

For Japan only: the rights of the Investigator / trial site and of the sponsor with regard to publication of the results of this trial are described in the Investigator contract / trial site's contract. As a general rule, no trial results should be published prior to finalisation of the Clinical Trial Report.

The certificate of insurance cover is made available to the Investigator and the patients, and is stored in the ISF (Investigator Site File).

8.1 TRIAL APPROVAL, PATIENT INFORMATION, INFORMED CONSENT

This trial will be initiated only after all required legal documentation has been reviewed and approved by the respective Institutional Review Board (IRB) / Independent Ethics Committee (IEC) and competent authority (CA) according to national and international regulations. The same applies for the implementation of changes introduced by amendments.

Prior to patient participation in the trial, written informed consent must be obtained from each patient (or the patient's legally accepted representative) according to ICH / GCP and to the regulatory and legal requirements of the participating country. Each signature must be personally dated by each signatory and the informed consent and any additional patient-information form retained by the Investigator as part of the trial records. A signed copy of the informed consent and any additional patient information must be given to each patient or the patient's legally accepted representative.”

For Japan only: The Investigator must give a full explanation to trial patients based on the patient information form. A language understandable to the patient should be chosen, technical terms and expressions avoided, if possible. The patient must be given sufficient time to consider participation in the trial. The Investigator obtains written consent of the patient's own free will with the informed consent form after confirming that the patient understands the contents.

For Japan only: The Investigator must sign (or place a seal on) and date the informed consent form. If a trial collaborator has given a supplementary explanation, the trial collaborator also signs (or places a seal on) and dates the informed consent.

Re-consenting may become necessary when new relevant information becomes available and should be conducted according to the sponsor's instructions.

The consent and re-consenting process should be properly documented in the source documentation.

8.2 DATA QUALITY ASSURANCE

A quality assurance audit/inspection of this trial may be conducted by the sponsor, sponsor's designees, or by IRB / IEC or by regulatory authorities. The quality assurance auditor will have access to all medical records, the Investigator's trial-related files and correspondence, and the informed consent documentation of this clinical trial.

8.3 RECORDS

Case Report Forms (CRF) for individual patients will be provided by the sponsor. See [Section 4.1.5.2](#) for rules about emergency code breaks. For drug accountability, refer to [Section 4.1.8](#).

8.3.1 Source documents

If defined in the protocol, additional records may need to be requested from the Investigator, e.g. information from any referral physicians on patient history relevant for AE reporting or data required in connection with outcome event collection in outcome studies.

In accordance with regulatory requirements the Investigator should prepare and maintain adequate and accurate source documents and trial records that include all observations and other data pertinent to the investigation on each trial subject. Source data as well as reported data should follow good documentation practices and be attributable, legible, contemporaneous, original and accurate. Changes to the data should be traceable (audit trail).

Data reported on the CRF must be consistent with the source data or the discrepancies must be explained.

The current medical history of the subject may not be sufficient to confirm eligibility for the trial and the Investigator may need to request previous medical histories and evidence of any diagnostic tests. In this case the Investigator must make three documented attempts to retrieve previous medical records. If this fails a verbal history from the patient, documented in their medical records, would be acceptable.

Before providing any copy of patients' source documents to the sponsor the investigator must ensure that all patient identifiers (e.g. patient's name, initials, address, phone number, social security number) have properly been removed or redacted to ensure patient confidentiality.

If the patient is not compliant with the protocol, any corrective action e.g. re-training must be documented in the patient file.

For the CRF, data must be derived from source documents, for example:

- * Patient identification: gender, date or year of birth (in accordance with local laws and regulations)
- * Patient participation in the trial (substance, trial number, patient number, date patient was informed)
- * Dates of Patient's visits, including dispensing of trial medication
- * Medical history (including trial indication and concomitant diseases, if applicable)
- * Medication history
- * Adverse events and outcome events (onset date (mandatory), and end date (if available))
- * Serious adverse events (onset date (mandatory), and end date (if available))
- * Concomitant therapy (start date, changes)
- * Originals or copies of laboratory results and other imaging or testing results, with proper documented medical evaluation (in validated electronic format, if available)
- * Completion of Patient's Participation in the trial" (end date; in case of premature discontinuation document the reason for it).
- * Prior to allocation of a patient to a treatment into a clinical trial, there must be documented evidence in the source data (e.g. medical records) that the trial participant meets all inclusion criteria and does not meet any exclusion criteria. The absence of records (either medical records, verbal documented feedback of the patient or testing conducted specific for a protocol) to support inclusion/exclusion criteria does not make the patient eligible for the clinical trial.

